6.1 Physician Selection Criteria

Approximately 450 physicians will participate in this trial. Approximately 185 physicians will be included based on participation in prior clinical development studies. An additional 265 physicians will be included based on their available eligible patient population.

6.2 Selection of Study Population

Patients meeting all of the inclusion criteria and who have none of the exclusion criteria may be enrolled.

6.2.1 Inclusion Criteria

An adult patient (18 years of age or older) with CD for whom Humira therapy is indicated according to the local product label and who meet the following criteria may be enrolled in this study:

1. Patients to be enrolled must fall into one of the following categories:
 - Patients who are newly prescribed Humira therapy (have never been treated with adalimumab).
 - Patients who are current participants in AbbVie sponsored investigational CD trials, are currently receiving Humira and for whom the treating physician has made the decision to continue with Humira therapy beyond the duration of the investigational trial.
 - Patients who were prior participants in AbbVie sponsored investigational Crohn's disease trials, who have not had dose interruptions since the last dose of registry drug, where the Investigator can provide source documentation of dosing information.
 - Patients who are currently receiving Humira, as per the local product label, who have not had dose interruptions since the induction dose of Humira where the Investigator can provide source documentation of dosing information.
2. Patients willing to consent to data being collected and provided to AbbVie.
3. Patients capable of and willing to give written informed consent and to comply with the requirements of the Registry protocol.

6.2.2 Exclusion Criteria

1. Patients should not be enrolled if they cannot be treated in accordance with the local product label.

6.2.3 Patient Follow-up Criteria

In order to participate in the follow-up process, patients who discontinued the Registry must re-consent to participation in the Registry or consent to participate in the direct to HCP process.

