In the controlled portions of clinical trials of TNF-antagonists, more cases of malignancies including lymphoma and non-melanoma skin cancer have been observed among patients receiving a TNF-antagonist compared with control patients. However, the occurrence was rare.¹² Furthermore, there is an increased background lymphoma risk in rheumatoid arthritis patients with long-standing, highly active, inflammatory disease, which complicates the risk estimation.¹³⁻¹⁵ Post-marketing cases of rare malignancies usually associated with immunosuppression and malignancies that are not usually observed in children and adolescents have been reported with use of TNF antagonists including adalimumab. These case reports are derived from a variety of sources including registries and spontaneous post-marketing reports.¹⁰ Rare post-marketing cases of hepatosplenic T-cell lymphoma have been identified in patients treated with TNF-antagonists including adalimumab.^{18,19} This rare type of T-cell lymphoma, has a very aggressive disease course and is usually fatal.¹⁶ Some of the cases reported for adalimumab occurred in young adult patients with inflammatory bowel disease who were also taking other oral medications, e.g., azathioprine, that can suppress the immune system. There have also been cases of acute and chronic leukemia reported in association with the use of TNF-antagonists including adalimumab. With the current knowledge, a possible risk for the development of lymphomas or other malignancies in patients treated with a TNF-antagonist cannot be excluded.

Patients with UC and CD involving the colon have a substantially increased risk of developing colorectal cancer. The risk for colorectal cancer in CD involving the colon is similar to that of UC of similar duration and extent. Small intestinal cancer occurs at an increased rate in patients with Crohn's enteritis, but the absolute risk remains small.

Extraintestinal malignancies are uncommon in IBD but lymphomas, biliary tract cancers and squamous cell cancers of the skin may occur at an increased rate in IBD patients.^{17,18}

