6.0 Investigational Plan

This is a multicenter, uncontrolled non-interventional Registry of patients with CD treated in a routine clinical setting with Humira. Approximately 5,000 subjects in the US, Europe, Canada, Australia, New Zealand and South Africa will be enrolled.

Physicians will be provided with a study kit that includes a protocol, patient informed consent forms, Serious Adverse Event Report Forms, paper patient questionnaires, and electronic Case Report Forms (eCRFs).

The decision to prescribe Humira (adalimumab) to the patients should be made separately from the decision to enroll them in the Registry.

With patient consent and having met all the inclusion criteria and none of the exclusion criteria, the physician may enroll the patient into the Registry. Physicians are encouraged to treat their patients as they would in their routine clinical practice and in accordance with the local Humira (adalimumab) product label. The physician will then follow the patient during regular office visits at intervals as determined by routine clinical practice or as recommended by national guidelines.

Patient's safety data and information about medications taken for CD will be recorded on eCRFs at study enrollment and during their regularly scheduled visits which are closest to Months 3, 6, 9, 12, 18, 24, 30, 36, 42, 48, 54, 60, 66 and 72. While the physician may deem it appropriate and necessary to have the patient return for intermediate visits during the course of the registry, data will be collected via eCRFs only at the intervals that most closely correspond to those described above.

In an effort to maximize safety data collection, physicians will be asked to do the following:

- Consent and re-enroll patients that were previously discontinued due to the prior P06-134 protocol withdrawal criteria (e.g., patient discontinued Humira). Patients that re-enroll in the Registry will resume data collection via the eCRF process as outlined in the protocol.
- For patients that re-enroll in the Registry, physicians will be asked to collect and report surgeries or hospitalizations and adverse events of special interest (Section 7.1.2) and Crohn's related medication use between registry discontinuation and re-enrollment based on a retrospective review of their patient records.

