- For patients that decline re-enrollment for full safety and effectiveness data collection or who have discontinued from the Registry for other reasons, physicians will be asked to obtain the patient's consent to data release for the completion of a simplified Healthcare Provider (HCP) questionnaire on an annual basis. The first data collection period will capture data from the time of patient's discontinuation of the Registry through the start of the direct to HCP process. The questionnaire focuses on the collection of surgeries or hospitalizations and adverse events of special interest and Crohn's related medication use since registry discontinuation. The questionnaire may be completed by the registry physician or the patient's current HCP (if they are no longer under the care of a registry physician). An HCP is not considered a participating investigator in the registry since they are only completing an annual questionnaire on behalf of a former registry patient. Participating registry investigators for which all of their patients have discontinued from registry participation may convert to an HCP status if their patients(s) choose to participate in the HCP process.

If treatment with Humira is permanently discontinued for any reason, patients will be encouraged to remain in the registry or to participate in the direct to HCP process unless consent is withdrawn.

When applicable, information about the effectiveness of Humira therapy will be provided by the patients and their physician. Effectiveness of therapy provided by the patient will be collected with PROs beginning with the registry enrollment visit, at regularly scheduled visits which are closest to Months 3, 6, 9, 12, and every 6 months thereafter, if part of routine clinical assessment. The following PROs will be used: Short Inflammatory Bowel Disease Questionnaire (SIBDQ), Health Care Resource Utilization (Unscheduled Outpatient Visits, Emergency Room Visits and Hospitalizations Questionnaire), and Work Productivity and Activity Impairment (WPAI). There are approximately 20 questions in the PRO assessments and it is expected that it will take approximately 15 minutes to complete them. Effectiveness of therapy will be collected through the Physician's Global Assessment beginning with the Registry enrollment visit and at regularly scheduled visits which are closest to Months 3, 6, 9, 12, and every

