10.0 Statistical Methods and Determination of Sample Size

10.1 Statistical and Analytical Plans

Analyzable Populations:

Safety Populations During the Registry:

The Registry Safety Population consists of all patients who received at least one dose of Humira (adalimumab) in the Registry. This will be the population for safety analyses in the Registry and include safety data collected during the Registry only.

The "Episodic Dosing" Population will consist of patients in the Registry Safety Population who:

- discontinue Humira (adalimumab) at least once for more than 70 days and receive at least one dose of adalimumab after the treatment interruption,
- do not receive any other biologics during the treatment interruption and,
- provide data before and after Humira (adalimumab) treatment interruption period(s)
- and include safety data collected during the Registry only.

For patients previously treated with commercial Humira before enrollment into the Registry, Day 1 of adalimumab treatment will be the 1st day of Humira therapy, i.e., before enrollment into the Registry. Detailed information on concomitant medications, safety and effectiveness between the 1st dose of Humir and enrollment into the Registry will be available for these patients.

Re-enrollment Safety Population:

The Re-enrollment Safety Population consists of all patients who were discontinued from the Registry due to prior protocol withdrawal criteria (i.e., patients who have discontinued Humira therapy) or discontinued for other reasons and re-consent to participation in the Registry. This will be the population for safety analyses of data collected during the re-enrollment period.

For patients that re-enroll in the Registry, safety information collected between registry discontinuation and re-enrollment based on a retrospective review of their patient records will be analyzed separately.

HCP Safety Population:

The HCP Safety Population consists of all patients that decline re-enrollment to participation in the Registry or who have discontinued from the Registry for other reasons and consent to data release for the completion of a simplified HCP questionnaire in the direct to HCP process. This will be the population for safety analyses of data collected on HCP questionnaire.

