10.5 Safety Analyses

For the Registry Safety Population, treatment-emergent SAEs and adverse events of interest will be summarized. Treatment-emergent SAEs and adverse events of interest are defined as: (1) new events that begin either on or after the first dose of Humira through the last dose of Humira plus 70 days; or (2) increase in severity of ongoing SAEs that had occurred before the first dose date of Humira. The number and percent of patients experiencing SAEs and adverse events of interest will be tabulated by body system and Medical Dictionary for Drug Regulatory Activities (MedDRA[®]) preferred term. The percent of patients will be presented with 95% confidence intervals. In addition, summary of SAEs and adverse events of interest by severity and relationship to registry drug will be presented.

The event rate of SAEs and of each adverse event of interest per 100 patient year of observation will be presented. Event rates will be presented with 95% confidence intervals. For patients enrolled from a prior CD study, the total number of SAEs and adverse events of interest will include the events reported during their participation in the previous study plus any events reports during the Registry.

In addition, Observational AEs: SAEs and AEs of interest occurring from the first dose of Humira in the registry through the last contact including re-enrollment period and during the HCP process will be tabulated.

For the 'Episodic Dosing' Population, following analyses will be provided:

- Summary of SAEs and AEs of special interest will be provided for patients with episodic dosing and without episodic dosing.

- Summary of SAEs and AEs of special interest will be provided before the treatment interruption and after the treatment interruption for patients with episodic dosing.
- For each SAE and AE of special interest, and each episodic dosing, a shift table to summarize number and percentage of patients who have the event or not before the treatment interruption and after the treatment interruption.

For the Re-enrollment Safety Population, the number and percent of patients experiencing SAEs and AEs of interest during the re-enrollment period will be tabulated by body system and MedDRA preferred term. In addition, the number and percent of patients experiencing SAEs and AEs of interest collected between registry discontinuation and re-enrollment based on a retrospective review of their patient records will be tabulated separately.

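### Post-discontinuation look-back data come only from patients who survived to consent again; the plan sets this time apart for re-enrolled patients but not for the HCP group or the observational window

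*Protocol*

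**What the plan says.** Follow-up after a patient leaves the registry depends on that patient's new agreement. Section 6.2.3 requires that "patients who discontinued the Registry must re-consent to participation in the Registry or consent to participate in the direct to HCP process". Section 6.0 adds that "physicians will be asked to obtain the patient's consent to data release for the completion of a simplified Healthcare Provider (HCP) questionnaire", and 6.4.1 repeats both consent routes. No proxy route is described.

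Once consent is given, collection goes backward. For re-enrolled patients, section 6.0 asks for surgeries, hospitalizations, adverse events of special interest and Crohn's medication "between registry discontinuation and re-enrollment based on a retrospective review of their patient records"; section 7.7 has the same scope. For the HCP route, section 6.0 says the first collection period "will capture data from the time of patient's discontinuation of the Registry through the start of the direct to HCP process".

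The two look-backs are then handled differently. Sections 10.1 and 10.5 analyze and tabulate the re-enrollment gap separately from the re-enrollment period. For the HCP Safety Population, 10.1 says: "This will be the population for safety analyses of data collected on HCP questionnaire". Section 10.5 provides one tabulation of everything collected on that questionnaire. It also tabulates Observational AEs "occurring from the first dose of Humira in the registry through the last contact including re-enrollment period and during the HCP process".

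Two other provisions bear on deaths. Section 6.5 plans reasonable efforts to learn vital status at the end of each patient's six years, and matching of patients lost to follow-up to death, cancer and vital registries. Section 7.4 collects events until at least 70 days after Humira stops.

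**The concern.** A patient who left the registry and died before being approached cannot consent, so neither that patient's gap time nor the fatal event enters the Re-enrollment or HCP population. A patient who lived and consents brings in the whole gap. Gap time in these populations is thus conditional on survival (immortal time).

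The events affected matter to a safety registry. The introduction reports fatalities and sepsis with TNF antagonists, and says hepatosplenic T-cell lymphoma "has a very aggressive disease course and is usually fatal". Section 4.0 gives the aim of the added follow-up as getting as much safety information as possible from all registry patients. Where survivor-only time is mixed with prospective time, a reader cannot tell which part of the follow-up was able to show a death. Any rate that counts the gap in its denominator would look more favorable than it should.

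**Working it through.** **Step 1: who can contribute gap data, and where the data go.**

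| | Re-enrolled patients | HCP patients |
|---|---|---|
| Entry condition | Own re-consent (6.2.3, 6.4.1) | Own consent to data release (6.0, 6.4.1) |
| Gap covered | Discontinuation to re-enrollment (6.0, 7.7) | Discontinuation to HCP start, the first collection period (6.0) |
| Can a fatal gap event appear? | No | No |
| Gap kept apart in the group's own analysis? | Yes (10.1, 10.5) | No (10.1, 10.5) |
| Gap excluded from the observational window? | Not stated | Not stated |

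The survival condition is the same in both columns, but only one column is separated. The first HCP collection period contains look-back data only, so the split is available in the data as collected. In the HCP tabulation in 10.5, the reference to the HCP process describes when data are collected, so look-back events are included.

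**Step 2: effect on percentages.** Let N be the consenting HCP patients, d those with a fatal event after consent, e those with a non-fatal event after consent, and g those whose only non-fatal event fell in the gap.

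- Fatal, with or without the look-back: d/N. Gap time is not in the denominator, so there is no dilution.
- Non-fatal: (e + g)/N with the look-back, e/N without it.

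The look-back therefore enlarges only the non-fatal side. The table mixes two observation windows, but the percentage with a fatal event is not lowered.

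**Step 3: effect on a rate per patient-year, if one counted gap time.** The base is the projection in section 10.7, reproduced first:

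- Attrition rate 0.231 per year, 6 years: (1 − e^(−0.231 × 6))/0.231 = 3.246 years per patient.
- 5,000 × 3.246 = 16,230 patient-years, as stated.

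With D deaths in T = 16,230 patient-years, the rate is D/T. Adding G gap patient-years in which no death can be recorded gives D/(T + G). The relative understatement is 1 − T/(T + G) = G/(T + G).

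The protocol gives neither the number returning nor the gap length. Both are assumed here:

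| Assumed returners × gap | G | G/(16,230 + G) |
|---|---|---|
| 500 × 1 year | 500 | 500/16,730 = 3% |
| 1,000 × 2 years | 2,000 | 2,000/18,230 = 11% |
| 2,000 × 3 years | 6,000 | 6,000/22,230 = 27% |

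These figures also assume that no other time is added. Prospective time after consent would enlarge the base and make each percentage smaller.

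**The case against.** The strongest reply is that the protocol plans no statistic that the gap would bias. Section 10.5 names no mortality rate. Its rates per 100 patient-years sit in the text on the Registry Safety Population, which 10.1 limits to data collected during the registry, and the treatment-emergent window closes 70 days after the last dose. The HCP and Re-enrollment outputs are counts and percentages of patients, and Observational AEs are only tabulated. Much of this stands. Nothing says that gap time enters a denominator, so 27% is no forecast. A reader might also infer that the apparent HCP death rate is halved, by supposing a 2-year gap followed by 2 years of questionnaires. That needs a rate the plan does not contain and durations it does not give.

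A reader might further infer that fatal gap events are lost to the registry altogether. The documents do not support this. The vital-status sentence in 6.5 is not restricted to patients lost to follow-up; only the registry matching is. A discontinued patient who has died may be unreachable after three attempts, be classed as lost, and so be matched. Section 7.4 covers at least the first 70 days off drug and sends later related events to post-marketing reporting. These safeguards are best-effort, the matching does not name patients who were reached and declined, and 10.5 links none of this to an analysis. How linked deaths are counted may properly be left to the SAP, so that silence alone is not a fault.

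Finally, the observational window can be read as skipping the gap, since it names the re-enrollment period and the HCP process, and 10.1 distinguishes the former from the time before it. But its stated ends are first registry dose and last contact, with no exclusion. The wording leaves both readings open.

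**Conclusion.** The point holds in a limited form. Gap data in the Re-enrollment and HCP populations are conditional on surviving to consent, and fatal gap events cannot appear in those populations. The plan separates this time for re-enrolled patients, but not for HCP patients, where the same condition applies, and it does not exclude it from the observational window.

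The consequence depends on the statistic. Percentages of patients with fatal events are not diluted. An observational rate per patient-year that counted the gap would be biased downward for fatal and rapidly fatal events. The amount cannot be derived from the protocol; the 11% illustration rests on an assumed 2,000 gap patient-years, on their entering the denominator, and on no other time being added. Prospective follow-up after consent is unaffected, and a patient who consents at discontinuation has no gap.

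**What to change.** In sections 10.1 and 10.5:

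- Tabulate the first HCP collection period separately from later HCP data, as is already done for the re-enrollment gap.
- For any observational rate per patient-year, stop follow-up at the original discontinuation, or at last dose plus 70 days if later, and resume it at re-consent or HCP consent (delayed entry). Report gap events in a separate table or as a sensitivity analysis.
- Show discontinued patients who did not return, by the vital status obtained under 6.5, beside these results.

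The cost is wording and programming, with no new data collection: consent forms are dated, withdrawal is noted on the study completion form, and the HCP look-back is already its own collection period. The real downside is that non-fatal gap events, including any lymphomas, leave the main pooled tabulation. That matters somewhat in a registry whose sample size rests on 17 lymphoma events, so the separate table should appear next to the pooled one.

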6.3 Safety and Effectiveness Variables/Schedule of Assessments

This is a long-term Registry with the objective of documenting safety and effectiveness of Humira in routine clinical practice.

6.3.1 Safety Variables

The physician will be asked to document serious adverse events and adverse events of interest on eCRFs (Section 7.5).

Serious adverse events and adverse events of interest as defined in Section 7.1.1 and Section 7.1.2 respectively, will be reported to AbbVie from the time the physician obtains the subject's authorization to use and disclose information (or the subject's informed consent) throughout the patient's participation in the Registry, up to 6 years. In the event adalimumab therapy is interrupted, SAEs and adverse events of interest will be collected throughout the interruption. If treatment with adalimumab is permanently discontinued for any reason, patients should be encouraged to continue in the registry or the direct to HCP process for a full 6 year observation period irrespective of future treatment decisions so important safety information can be obtained, as outlined in Section 6.0.

SAE reports will be completed and submitted using an electronic version of AbbVie's standard SAE form (Section 7.5).

Additional information on the adverse events of interest will be collected on separate data collection forms. These forms will capture specific information relevant to the event of interest.

In case of pregnancy, AbbVie must be notified within 1 working day of a site's learning if a female subject becomes pregnant during the registry. No clinical data on the use of adalimumab in pregnant women is available. For details please refer to the product prescribing information. Information regarding the outcome of any pregnancy occurring in a registry patient will be collected (Section 7.6). Patients who become pregnant and interrupt their Humira (adalimumab) therapy may remain in the Registry.

